7.2.2 Permitted concomitant medications

Table 2. Supportive medications

Supportive medication/class of drug:	Usage:
Concomitant medications or treatments (e.g., acetaminophen or diphenhydramine) deemed necessary to provide adequate prophylactic or supportive care, except for those medications identified as “prohibited,” as listed below	To be administered as prescribed by the Investigator
Best supportive care (including antibiotics, nutritional support, correction of metabolic disorders, optimal symptom control, and pain management [including palliative radiotherapy to non-target lesions, etc])	Should be used, when necessary, for all patients
Inactivated viruses, such as those in the influenza vaccine	Permitted

7.2.3 Excluded concomitant medications

Table 3. Prohibited concomitant medications

Prohibited medication/class of drug:	Usage:
Any investigational anticancer therapy other than those under investigation in this study	Should not be given concomitantly whilst the patient is on study treatment
mAbs against CTLA-4, PD-1, or PD-L1 other than those under investigation in this study	Should not be given concomitantly whilst the patient is on study treatment
Any concurrent chemotherapy, radiotherapy, immunotherapy, or biologic or hormonal therapy for cancer treatment other than those under investigation in this study	Should not be given concomitantly whilst the patient is on study treatment. (Concurrent use of hormones for non-cancer-related conditions [e.g., insulin for diabetes and hormone replacement therapy] is acceptable. Local treatment of isolated lesions, excluding target lesions, for palliative intent is acceptable [e.g., by local surgery or radiotherapy])
Immunosuppressive medications including, but not limited to, systemic corticosteroids at doses exceeding 10 mg/day of prednisone or equivalent, methotrexate, azathioprine, and tumor necrosis factor- α blockers	Should not be given concomitantly or used for premedication prior to the I-O infusions. The following are allowed exceptions: 
• Use of immunosuppressive medications for the management of IP-related AEs,• Use in patients with contrast allergies.• In addition, use of inhaled, topical, and intranasal corticosteroids is permitted. A temporary period of steroids will be allowed if clinically indicated and considered to be essential for the management of non-immunotherapy related events experienced by the patient (e.g., chronic obstructive pulmonary disease, radiation, nausea, etc).
Drugs with laxative properties and herbal or natural remedies for constipation	Should be used with caution through to 90 days after the last dose of tremelimumab during the study
Sunitinib	Should not be given concomitantly or through 90 days after the last dose of tremelimumab (acute renal failure has been reported with combination therapy of tremelimumab and sunitinib)

Prohibited medication/class of drug:	Usage:
EGFR TKIs	Should not be given concomitantly. Should be used with caution in the 90 days post last dose of durvalumab. Increased incidences of pneumonitis (with third generation EGFR TKIs) and increased incidence of transaminase increases (with 1 st generation EGFR TKIs) has been reported when durvalumab has been given concomitantly.
Live attenuated vaccines	Should not be given through 30 days after the last dose of IP (including SoC)
Herbal and natural remedies which may have immune-modulating effects	Should not be given concomitantly unless agreed by the sponsor

8. STUDY PROCEDURES

8.1 Schedule of study procedures

Before study entry, throughout the study, and following study drug discontinuation, various clinical and diagnostic laboratory evaluations are outlined. The purpose of obtaining these detailed measurements is to ensure adequate safety and tolerability assessments. Clinical evaluations and laboratory studies may be repeated more frequently if clinically indicated. The Schedules of Assessments during the screening and treatment period is provided following the Protocol Synopsis

For all patients

- Tumor efficacy (modified RECIST) assessment dates are affected by dose delays as subsequent treatment with DEB-TACE will be delayed with the same interval change.
- All other scheduled assessments must be performed relative to the start of the dosing cycle such that all laboratory procedures, etc. required for dosing should be performed within 3 days prior to dosing.
- Patients may delay dosing under certain circumstances.
 - Dosing may be delayed per Toxicity Management Guidelines, due to either an immune or a non-immune-related AE.
 - If dosing must be delayed for reasons other than treatment-related toxicity, dosing will resume as soon as feasible

8.1.1 Screening phase

Screening procedures will be performed up to 28 days before Day 1, unless otherwise specified. All patients must first read, understand, and sign the IRB/REB/IEC-approved ICF before any study-specific screening procedures are performed. After signing the ICF, completing all screening procedures, and being deemed eligible for entry, patients will be enrolled in the study. Procedures that are performed prior to the signing of the ICF and are considered standard of care may be used as screening assessments if they fall within the 28-day screening window. See **Figure 2** for all screening procedures.

Figure 2 : Study Schedule

Week	Pre-study (Day -28 to Day 0)	0	1	2 +/- 7d	6 +/- 7d	8 +/- 7d	9 ^a	10 +/- 7d	14 +/- 7d	16 +/- 7d	17 ^a	Weeks 18, 22, 26, 30, 34, 38, 42, 46, 50 +/- 7d	17-52	Time since last dose of Durvalumab				Q6 months +/- 2 wks
		EOT ^b 30 days +/- 7d	2 months +/- 7d	3 months +/- 7d	6, 9, 12 months +/- 2 wks													
TACE ^a		X				X ^a				X ^a								
Durvalumab				X	X			X	X			X						
Tremelimumab				X														
Informed Consent	X																	
Demographics	X																	
Medical history	X																	
Physical exam ^b and Vital signs ^c	X		X	X	X		X	X	X		X	X						
Concomitant Meds	X		X	X	X	X	X	X	X	X	X	X						
Adverse Event Evaluation ^d	X		X	X	X	X	X	X	X	X	X	X						
ECOG Performance Status	X		X	X	X		X	X	X		X	X						
Hepatology Visits			X			X				X	X							
Oncology Visits	X			X	X			X	X			X						
MRI / CT ^e	X			X				X				X ^e						
ECG ^f	X		X															
Urinalysis ^g	X																	
CMP ^h	X			X	X	X		X	X	X		X						
CBC with differentials ^h	X			X	X	X		X	X	X		X						
PT, INR, PTT ^{h, i}	X			X	X	X		X	X	X		X						
Thyroid Panel ^{h, j}	X			X	X	X		X	X			X						
Creatinine clearance ^h	X																	
Magnesium ^h	X																	
Gamma-glutamyl transferase (GGT) ^h	X																	
Alpha-fetoprotein (AFP) ^h	X			X	X			X	X			X						
Amylase/Lipase ^h	X																	
LDH ^h	X																	
HBV, HCV, HIV ^{h, k}	X			X ^k	X ^k			X ^k	X ^k			X ^k						
HLA-A,B,C phenotyping	X																	

Urine hCG or serum β hCG ¹	X													
Research Blood ^{m, p}		X	X	X									X	
Research urine ^{m, p}		X	X	X									X	
Liver Biopsies ^p		X	X	X										
Archival Tissue ^q					X									
Subsequent anticancer therapy ⁿ													X	X
Survival Status ⁿ													X	X

In order to minimize the need for research-only in-person visits, telemedicine visits may be substituted for in-person clinical trial visits or portions of clinical trial visits where determined to be appropriate and where determined by the investigator not to increase the participants risks. Prior to initiating telemedicine for study visits the study team will explain to the participant, what a telemedicine visit entails and confirm that the study participant is in agreement and able to proceed with this method. In the event telemedicine is not deemed feasible, the study visit will proceed as an in-person visit. Telemedicine visits will be conducted using HIPAA compliant method approved by the Health System and within licensing restrictions.

- a. DEB-TACE will be repeated every 8 weeks as long as there is residual tumor that can be targeted after the first dose (we expect most patients will receive at least 2 doses, and more than 3 doses of DEB-TACE are possible). Patients with a complete response by mRECIST will stop DEB-TACE and continue the rest of the study regimen. When DEB-TACE will no longer be given, the entire DEB-TACE visit and evaluations (e.g. Week 16) and follow-up visit 1 week after the skipped DEB-TACE (e.g. Week 17) may be dropped.
- b. Full physical examination at baseline; targeted physical examination at other time points
- c. Patients will have their blood pressure and pulse measured before, during, and after the infusion at the following times (based on a 60-minute infusion):
 - At the beginning of the infusion (at 0 minutes)
 - At 30 minutes during the infusion (\pm 5 minutes)
 - At the end of the infusion (at 60 minutes \pm 5 minutes)
- d. for AEs/SAEs reported during prescreening additional information such as medical history and concomitant medications may be needed.
- e. **Timing of MRI/CTscans:** Scans at baseline and Week 6 (+/- 7 days), then every 8 weeks (+/- 7 days) for the first 15 weeks, then every 3 months (-3/+1 weeks) unless repeat TACE is done. Scans may be done earlier if clinically indicated and subsequent scans should reset to every 3 months from this new scan date when possible. EOT tumor assessments do not need to be repeated if performed within 28 days of EOT visit. **For patients who have completed study treatment and achieved disease control:** tumor assessments should be performed every 8-12 weeks until confirmed PD by mRECIST by investigational site. **For patients who discontinue study treatment due to PD:** tumor assessments should be performed according to local clinical practice and may be submitted to investigational site for review (these are optional).
- f. ECG during screening and at the Week 2 visit within 1hr prior to the start of the first study treatment. Thereafter as clinically indicated. Baseline and abnormal ECG at any time in triplicate, others single.
- g. Urinalysis performed at Screening and as clinically indicated
- h. Labs and research bloods may be done within 3 days of scheduled visits. Results for safety bloods must be available and reviewed before commencing an infusion.
- i. Coagulation tests: prothrombin time done at each indicated visit., aPTT and INR only performed at Screening and as clinically indicated.
- j. TSH only. Free T3 and free T4 will be measured if TSH is abnormal or if there is clinical suspicion of an adverse event related to the endocrine system.
- k. **Screening:** HBV surface antigen (HBsAg), anti-HBV core antibody (anti-HBc), anti-HCV antibody, and HIV-1/2 Ab. HBV viral load if HBsAg and/or anti-HBc positive. Hepatitis serologies do not need to be repeated if done within 3m prior to enrollment. **On Study Labs:** HBV antigen and/or antibody positive patients allowed to participate per eligibility criteria will have HBV viral load monitored prior to each subsequent durvalumab treatment visit.
- l. Pre-menopausal female patients of childbearing potential only
- m. Approximately 40 ml of blood and 100 ml urine will be collected at 4 time points (Week 0, Week 2, Week 8, and at end of study. Blood and urine should be collected before any treatment.
- n. Patients will be contacted for survival status and information about subsequent anticancer therapies (by phone, email, or visit) monthly for the first 3 months after last dose of study treatment, then every 3 months until 1 year, then every 6 months thereafter until study closes or patient withdraws from follow-up.
- o. All required EOT procedures may be completed within \pm 7 days of the end of treatment visit (EOT). Repeat disease assessment is not required if performed within 28 days prior to the end of treatment visit.
- p. Research samples will be collected at the discretion of the PI based on availability of supplies and safety of patient and staff. If patient not deemed candidate for TACE on week 8, we will still collect biopsy, research blood/urine samples. These blood/urine samples can be obtained any time prior to or including at the next in person treatment visit. Biopsy should be obtained through IR at week 8 (+/-14 days).

q. Archival tissue samples may be collected if patient had a standard of care biopsy of tumor or non-tumor liver or other HCC metastatic sites (see section 8.3.2)

8.1.2 Treatment phase

Procedures to be conducted during the treatment phase of the study are presented in the Schedule of Assessments.

Patients will be treated with DEB-TACE. Transarterial chemoembolization is percutaneous procedure performed under conscious sedation. (See **Section 5.3** for details). Following DEB-TACE, patients will have surveillance imaging at 7 weeks, and if there are viable tumor lesions that can be targeted by DEB-TACE (either SD or PR), patients will be scheduled for another procedure. We estimate that patients may receive up to 4 DEB-TACE treatments in 1 year time of the study.

From the time of first DEB-TACE, patients will receive their first combined immune checkpoint inhibition in 2 weeks, and continue with q4week cycle schedule as described in detail in **Section 3.1**.

8.1.3 End of treatment

End of treatment (EOT) visit is defined as approximately 30 days after the last dose of study treatment. All required procedures may be completed within ± 7 days of the end of treatment visit. Repeat disease assessment is not required if performed within 28 days prior to the end of treatment visit.

Assessments for patients who have completed durvalumab and tremelimumab treatment are provided in the Study Schedule above.

All patients will be followed for survival and subsequent anti-cancer therapies until the end of the study regardless of further treatments.

8.2 Description of study procedures

8.2.1 Medical history

Findings from medical history (obtained at screening) and physical examination shall be given a baseline grade according to the procedure for AEs. Increases in severity of pre-existing conditions during the study will be considered AEs, with resolution occurring when the grade returns to the pre-study grade or below.

Physical examinations will be performed on study days noted in the Schedule of Assessments.

8.2.2 Physical examination

Physical examinations will be performed according to the assessment schedule. Full physical examinations will include assessments of the head, eyes, ears, nose, and throat and the respiratory, cardiovascular, GI, urogenital, musculoskeletal, neurological, dermatological, hematologic/lymphatic, and endocrine systems. Height will be measured at Screening only. Targeted physical examinations are to be utilized by the Investigator on the basis of clinical

observations and symptomatology. Situations in which physical examination results should be reported as AEs are described in **Section 10**.

8.2.3 MRI or CT

Patients will be recommended to have an MRI at week 6 following their first DEB-TACE date. If MRI is contraindicated for any medical reasons (e.g. history of metals in the body, severe claustrophobia), patients may have a CT scan (liver-dedicated CT). Tumor response will be assessed according to the modified RECIST criteria (mRECIST). mRECIST takes into account reduction in viable tumor using contrast-enhanced radiologic imaging rather than strict tumor size. Details of response measurement are under Section 9. If there is complete response at the 1st surveillance imaging, patients will continue with their monthly infusion with durvalumab and tremelimumab for total of 4 cycles, with repeat MRI as scheduled at week 14. If there's ongoing CR, they will have MRI monitoring every 3 months. For all other response after the 1st MRI, patients will get repeat DEB-TACE, along with scheduled immunotherapy treatment and scans per the study schedule.

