- Judgment by the investigator that the patient is unsuitable to participate in the study and the patient is unlikely to comply with study procedures, restrictions and requirements.

Investigational Product(s), Dose, and Mode of Administration:

Durvalumab 1500mg Q4W plus tremelimumab 300mg once via IV infusion, starting at 2 weeks after first DEB-TACE procedure. This will be followed by durvalumab monotherapy 1500 mg via IV infusion Q4W, until progression or unacceptable toxicity (maximum 13 doses/cycles).

Study Assessments and Criteria for Evaluation:

Safety Assessments:

To ensure that the combination is safe, the first six patients will be treated and observed for toxicity for 1 cycle before continuation with further accrual. If ≤ 1 limiting toxicity events occur in the first 6 patients, we will proceed with additional accrual to complete a total of 20 patients for the safety evaluation. If > 1 limiting toxicity events occur among the first 6 patients, then three additional patients will be enrolled (i.e. a total of 9 patients). If ≤ 2 limiting toxicity events occur in the 9 patients, we will proceed with additional accrual to complete a total of 20 patients for the safety assessment. If > 2 limiting toxicity events occur, we will pause the enrollment pending safety review.

Efficacy Assessments:

The primary endpoint is objective response using modified RECIST (mRECIST) criteria. The regimen would be considered of insufficient activity for further study if the response rate is 30%

or less, and the minimum required level of efficacy that would warrant further study with the proposed regimen is a 60% response rate.

Statistical Methods and Data Analysis:

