1.3.5.2 Rationale for 4 cycles of combination therapy followed by durvalumab monotherapy

Long-term follow up on melanoma patients treated with ipilimumab, an anti-CTLA-4 targeting antibody (dosed every 3 weeks [q3w] for 4 doses and then discontinued), shows that patients responding to ipilimumab derive long-term benefit, with a 3-year OS rate of approximately 22%. Furthermore, the survival curve in this population reached a plateau at 3 years and was maintained through 10 years of follow up (Sangro et al., 2013; Schadendorf et al., 2015).

Similar data have been presented for other anti-PD-1/PD-L1 targeting antibodies:

Nivolumab (anti-PD-1) was dosed q2w for up to 96 weeks in a large Phase I dose-escalation and expansion study, and showed responses were maintained for a median of 22.94 months for

melanoma (doses 0.1 mg/kg to 10 mg/kg), 17 months for NSCLC (doses 1, 3, and 10 mg/kg), and 12.9 months for renal cell carcinoma patients (doses 1 and 10 mg/kg) at the time of data analysis (Gettinger et al., 2015). Furthermore, responses were maintained beyond treatment discontinuation in the majority of patients who stopped nivolumab treatment (either due to protocol specified end of treatment, complete response [CR], or toxicity) for up to 56 weeks at the time of data analysis (Topalian et al., 2014) MPDL3280a (anti-PD-L1) and the combination of nivolumab with ipilimumab, in which patients were dosed for a finite time period and responses maintained beyond treatment discontinuation have been reported (Wolchok et al., 2013).

Similar long term results may be expected with use of other immune-mediated cancer therapeutics including anti-CTLA-4 antibodies such as tremelimumab, anti-PD-L1 antibodies such as durvalumab, or the combination of the two.

The durvalumab + tremelimumab combination regimen will be administered for 4 doses Q4W followed by durvalumab monotherapy Q4W until disease progression, for up to a maximum further 8 doses unless other specific discontinuation criteria are met.

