3. STUDY DESIGN

This is an open-label, single institution, single arm study of combination treatment of durvalumab and tremelimumab in patients with intermediate stage HCC (BCLC B) undergoing trans-arterial chemoembolization.

Patients will be recruited from the Johns Hopkins Multidisciplinary Liver Cancer Clinic, general liver clinic, inpatient admissions with newly diagnosed HCC, and direct referrals to Interventional Radiology for DEB-TACE treatment. Once their diagnosis and staging is confirmed in Liver radiology tumor board as intermediate stage, patients will be screened for enrollment.

Enrolled patients will proceed with DEB-TACE procedure along with pre-treatment biopsy of tumor and surrounding non-tumor tissue. Following their DEB-TACE procedure, patients will be followed in 7-10 days in hepatology clinic with labs for any new decompensating signs or symptoms. If the patient does not have any ongoing new decompensation, they will proceed with a 2nd biopsy, followed by 1st infusion of durvalumab 1500mg and tremelimumab 300mg 2 weeks after DEB-TACE. This will be followed by durvalumab 1500mg q4weeks until progression of disease, the end of study, or maximum 13 cycles.

All patients will receive repeat DEB-TACE every 8 weeks if there is residual tumor that can be targeted. A third biopsy will be done after 2 doses of durvalumab infusion during their second DEB-TACE procedure at week 8, unless the patient has CR.

Patients will have an MRI (or CT if contraindicated) at Week 6 and Week 14, then every 3 months unless additional DEB-TACE is needed. Patients who are clinically stable at initial disease progression may continue to receive study treatment until PD is confirmed on a follow-up scan (confirmed PD) if they do not show any significant toxicities. Patients will get a confirmatory scan, following the assessment of PD, at the next scheduled visit. Patients will continue to receive durvalumab and tremelimumab with the same dose and schedule as they were treated with initially.

Additionally, 20 patients from the institutional database will be selected as exact matched control based on age, gender, tumor stage and Child-Pugh score. We will evaluate the objective response rate (ORR) in comparison to the study group, using McNamer paired-sample test.

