5.2.1 Treatment regimens

All patients in this study will receive durvalumab and tremelimumab 2 weeks after initial DEB-TACE treatment. Patients will subsequently continue with their combination immunotherapy, while receiving DEB-TACE Q8W. Patients will only receive repeat DEB-TACE if there is residual tumor that can be targeted.

[figure not shown]
[figure not shown]

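### Five sections still describe or presuppose repeated tremelimumab dosing, contradicting the operative regimen of tremelimumab 300 mg once with up to 13 durvalumab doses

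*Combined protocol and SAP*

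**What the plan says.** The operative regimen is stated consistently where treatment is laid out. The synopsis, under investigational products, gives "Durvalumab 1500mg Q4W plus tremelimumab 300mg once via IV infusion, starting at 2 weeks after first DEB-TACE procedure", then durvalumab alone to a maximum of 13 doses. Section 3 describes the first combined infusion and adds "This will be followed by durvalumab 1500mg q4weeks until progression of disease, the end of study, or maximum 13 cycles". Section 1.3.5.1 concludes that the single 300 mg dose is what this study evaluates. Figure 2 marks tremelimumab once, at Week 2. It marks durvalumab at Weeks 2, 6, 10 and 14 and then at "Weeks 18, 22, 26, 30, 34, 38, 42, 46, 50 +/- 7d". Footnote a to Figure 2 covers complete responders: "Patients with a complete response by mRECIST will stop DEB-TACE and continue the rest of the study regimen".

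Five places in the current text say something else.

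- Section 8.2.3, for complete responders at the first scan: "patients will continue with their monthly infusion with durvalumab and tremelimumab for total of 4 cycles, with repeat MRI as scheduled at week 14".
- Section 1.3.5.2: "The durvalumab + tremelimumab combination regimen will be administered for 4 doses Q4W followed by durvalumab monotherapy Q4W until disease progression", and then "for up to a maximum further 8 doses".
- Section 1.3.5.3 lists 300 mg tremelimumab once and also 75 mg every four weeks as included in this study.
- Section 6.3 describes the 20 mg/kg durvalumab plus 1 mg/kg tremelimumab cohort and says that this is the dose level the study will give. It equates that level with 75 mg tremelimumab every four weeks.
- Section 9.1 lets patients who progress on durvalumab alone restart the combination, on condition that they completed four combination doses.

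**The concern.** The single tremelimumab dose defines this regimen. Section 1.3.5.1 chooses it for its higher peak exposure and for the possibility of avoiding cumulative toxicity from repeated dosing. Text that repeats tremelimumab therefore contradicts the reason for the regimen.

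Three of the five places are in operative sections. Section 8.2.3 is a patient-level instruction for complete responders. Section 6.3 introduces the definition of unacceptable toxicity with favourable adverse-event experience at a tremelimumab dose the trial does not give. Section 9.1 sets a retreatment condition that the operative regimen cannot satisfy.

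At stake are a dosing error and a safety rationale tied to the wrong dose. Two further details add to this. Section 10.3.12.1 defines overdose against the dose the protocol specifies, and the protocol specifies more than one. Section 6.3 ends the unacceptable-toxicity window at the Week 6 evaluation, before the second durvalumab dose, so tremelimumab repeated on the monthly schedule would fall outside that window.

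**Working it through.** **1. Reproduce the stated maximum.** Inputs: the durvalumab visits in Figure 2. Weeks 2, 6, 10 and 14 give 4 doses, and Weeks 18 to 50 at four-week steps give 9. 4 + 9 = 13, which matches the synopsis and Section 3. Tremelimumab: 1 dose. The correct split is 1 combined dose + 12 durvalumab doses = 13.

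**2. Section 1.3.5.2.** 4 combination doses + 8 further durvalumab doses = 12 durvalumab doses, not 13. On a four-week cycle from Week 2 the 12th dose falls at 2 + 4 × 11 = Week 46 and the 13th at 2 + 4 × 12 = Week 50. The section also implies 4 tremelimumab doses, where the schedule has 1.

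**3. Section 8.2.3.** Four monthly infusions fall at Weeks 2, 6, 10 and 14. For durvalumab, that count agrees with the schedule up to the Week 14 scan. For tremelimumab it does not, because the schedule has one infusion, at Week 2. The conflict lies in naming tremelimumab as a monthly infusion.

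**4. Sections 1.3.5.3 and 6.3.** Dose per administration: 300 / 75 = 4-fold. At the 75 kg body weight that the protocol uses, 300 / 75 = 4 mg/kg, against the 1 mg/kg named in Section 6.3. Predicted peak concentrations in Section 1.3.5.1 are 78 mcg/mL after a single 4 mg/kg dose, and 19 (first dose) and 25 (fourth dose) mcg/mL at 1 mg/kg every four weeks. The ratios are 78 / 19 = 4.1 and 78 / 25 = 3.1. Given four times, the 75 mg dose totals 4 × 75 = 300 mg, the same cumulative amount at a lower peak. Section 1.3.5.1 also says that no clinical data on the 300 mg regimen were available when the protocol was drafted. The experience cited in Section 6.3 therefore comes from a different dose.

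**5. Section 9.1.** The condition for restarting is four completed combination doses. The operative regimen has one, so no patient on it can meet the condition.

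**6. Effect on the primary analysis.** With first-stage size 8 (stop at 2 or fewer responses) and total size 20 (fail at 8 or fewer), exact binomial sums give type I error 0.0999 (stated 0.1), power 0.912 (stated 90%) and early-stopping probability 0.552 at a 30% response rate (stated 0.55). None of these depends on the dosing text.

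**The case against.** The synopsis, Sections 1.3.5.1 and 3 and Figure 2 agree, and staff will probably follow the schedule. Sections 1.3.5.2 and 1.3.5.3 are background, and the latter also states 300 mg once. The bodies of Sections 5.2.2 and 6.2 are not visible in the supplied text and may state the dosing and retreatment rules correctly. The toxicity criteria in Section 6.3 do not depend on the tremelimumab dose, the safety run-in tests whatever is actually given, and Section 1.3.5.1 openly discloses the lack of clinical data. All of that stands, and it limits the weight of the point. It does not remove the contradictions: a correct rule elsewhere leaves the conflicting text in force, and no rule of precedence is visible.

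Stronger readings are tempting, but the documents do not support them.

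- A reader might infer that Section 8.2.3 ends durvalumab at Week 14 in complete responders, with consequences for duration of response, progression-free survival and overall survival. The section never says that durvalumab stops. Its four cycles can simply count the infusions up to the Week 14 scan, and footnote a says that the rest of the regimen continues.
- A reader might infer a fourfold cumulative overdose from four doses of 300 mg. No section prescribes that. It would join the dose from one place to the count from another.
- A reader might count the sentences in the synopsis and Section 3 on treatment after progression as further contradictions. They refer to the initial dose and schedule, which for tremelimumab is once. The similar sentence in Section 9.1 can be read as using the two drug names for the regimen.
- Section 5.2.1 says "Patients will subsequently continue with their combination immunotherapy, while receiving DEB-TACE Q8W". It names no second tremelimumab dose, and the text around it is missing from the supplied copy, so it is unclear rather than contradictory.

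**Conclusion.** Wrong as written: an internal inconsistency in dosing text at five places (Sections 8.2.3, 1.3.5.2, 1.3.5.3, 6.3 and 9.1). Its size is one tremelimumab dose against four, 13 durvalumab doses against 12, and 300 mg once against 75 mg every four weeks, with a 3.1- to 4.1-fold difference in predicted peak concentration. The consequence is a risk of dosing error and a safety rationale in Section 6.3 that describes a different tremelimumab dose. The number of patients exposed to that risk cannot be stated, because the documents give no rate of complete response at the first scan. The response rate, the Simon decision rule and the sample size are untouched.

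The conclusion takes the regimen common to the synopsis, Sections 1.3.5.1 and 3 and Figure 2 as the intended one. It does not depend on what Sections 5.2.2 and 6.2 contain.

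**What to change.** - **Section 8.2.3:** state that patients in complete response at the first scan stop DEB-TACE and stay on durvalumab 1500 mg every four weeks, with no further tremelimumab, until progression, unacceptable toxicity or 13 durvalumab doses in total.
- **Section 1.3.5.2 (heading and last paragraph):** one combined dose, then up to 12 durvalumab doses.
- **Section 1.3.5.3:** delete the 75 mg tremelimumab regimen.
- **Section 6.3:** give the study dose as 300 mg once, and say that the 1 mg/kg experience comes from a different tremelimumab dose.
- **Section 9.1:** remove the four-dose condition and align retreatment after progression with Section 5.2.2.

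Optionally, clarify in Section 5.2.1 that durvalumab alone continues after the first infusion, and list the tremelimumab doses received by each patient.

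The cost is wording edits in five sections and, if the options are taken, one further edit and one listing from dosing records. No new data, patients or analyses are needed.
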